All subjects who discontinue from treatment should remain in the study and comply with protocol-specified follow-up procedures. The only exception to this requirement is when a subject withdraws consent for all study procedures or loses the ability to consent freely (ie, is imprisoned or involuntarily incarcerated for the treatment of either a psychiatric or physical illness).

Subjects lost to follow-up are defined by: 1) unable to reach the subject after three documented phone calls, fax, email or attempts to contact him/her through subject locator agencies (if allowed per national regulation); and 2) having sent one letter by registered/certified mail; all should be documented in the subject's medical records.

MRI-PDFF

A MRI-PDFF sub-study will be conducted at approximately 11 MRI sites in Europe. Approximately 60 (30 per arm) subjects from selected recruiting sites are expected to participate in the MRI-PDFF sub-study. Each subject participating in the MRI sub-study will be referred to a MRI site for MRI measurements. Several recruitment sites can refer subjects to one MRI site. Subjects participating in the MRI-PDFF sub-study will be required to provide informed consent. The date of these MRI assessments need not be the same as for Visit 1, but should be performed before Visit 3.

All subjects suitable for the study, including the MRI-PDFF sub-study, will be screened and recruited by the recruiting sites (sites treating subjects with T2DM). The recruiting investigator will be the main point of contact for the subject and also responsible for the documentation of study data within the eCRF. All subjects should have MRI visits scheduled to coincide with randomization, Week 52, and Week 122.

All MRIs will be sent for central evaluation to a core laboratory. No local reading will be performed. The results will be kept blinded to recruiting sites, the MRI sites, the subjects, and the Sponsor until the study is completed.

Continuous Glucose Monitoring (CGM)

[figure not shown]

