3.6 Post-Study Drug Study Follow up

In this study, safety is a key endpoint of the study. Post-study follow-up is of critical importance and is essential to preserving subject safety and the integrity of the study. Subjects who discontinue study drug must continue to be followed for collection of outcome and/or survival follow-up data as required, and in line with [Section 5](#), until death or the conclusion of the study.

Therefore, all subjects who discontinue IMP in the 52 week double-blinded short-term treatment period or in the long-term treatment period should be asked to continue study participation for each scheduled visit for the remaining length of the study and complete all procedures as outlined in [Section 5 \[Table 5.1-4\]](#) study flowchart, with the exception of study drug management. If continued study participation according to the protocol schedule is not possible, the investigator should contact the Sponsor to discuss alternatives (eg, return to the clinic 4 weeks after discontinuation of study drug to perform the Week 56 post-treatment follow-up procedures as outlined in [Section 5 \[Table 5.1-4\]](#) study flowchart or be contacted by telephone 4 weeks after discontinuation of study drug to evaluate the following safety assessments: AEs and hypoglycemia events. Please note that after the discontinuation of study drug, the management of the subject's diabetes will be under the care and direction of the investigator.)

The only exception to any of these follow-up methods are when a subject withdraws consent for all study procedures, including post-treatment study follow-up or loses the ability to consent freely (ie, is imprisoned or involuntarily incarcerated for the treatment of either a psychiatric or physical illness).

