3.6.1 Withdrawal of Consent

Subjects who request to discontinue study drug will remain in the study and must continue to be followed for protocol-specified follow-up procedures. The only exception to this is when a subject specifically withdraws consent for any further contact with him/her or persons previously authorized by the subject to provide this information. Subjects should notify the investigator of the decision to withdraw consent from future follow-up **in writing**, whenever possible. The withdrawal of consent should be explained in detail in the medical records by the investigator, as to whether the withdrawal is from further treatment with study drug only or also from study procedures and/or post treatment study follow-up, and entered on the appropriate eCRF page. In

the event that vital status (whether the subject is alive or dead) is being measured, publicly available information should be used to determine vital status only as appropriately directed in accordance with local law.

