8.4.2.2 Secondary Efficacy Analyses

In order to protect the overall type I error rate, the interpretation of the statistical significance of treatment comparisons for each secondary efficacy endpoint will be done using a step-wise procedure as outlined in [Section 8.4.2](#).

The analysis of change from baseline for total body weight and systolic blood pressure will be performed using the same longitudinal repeated measures model as for the primary efficacy endpoint.

The proportion of subjects achieving a therapeutic glycemic response (defined as HbA1c < 7.0%) at Week 52 and Week 156 will be summarized by treatment group and compared between treatment groups using logistic regression with adjustment for baseline HbA1c. The 95% confidence intervals for the response rate within each treatment group, odds ratio, and 95% confidence intervals for odds ratio will be calculated. Subjects who are rescued, discontinued or have missed measurements at Week t (t = 52 and 156, respectively) will be considered not achieving glycemic response.

Time to treatment intensification will be analyzed using a Cox proportional hazards model. Estimates of the hazard ratio and 95% confidence intervals will be provided. Kaplan-Meier estimates will be calculated and plotted by treatment group. For the analysis during 52 / 156 weeks, all subjects will be censored at 52 / 156 weeks if treatment intensification has not occurred by then. Subjects rescued at Week 52 / 156 will be counted as having an event for the analysis.

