7.1.1.3 Handling of Missing Data

The main analysis for change from baseline specified for primary and secondary endpoints in following sections will use the repeated measures model.

Safety analyses include either subjects’ data “prior to rescue medication”, or “regardless of rescue medication”. For analyses based on “prior to rescue medication”, subjects’ data up to and on the date of the first dose of rescue medication, subject to the prescribed cut off of the IP treatment

discontinuation (see Section 0), will be used. For analyses based on “regardless of rescue medication”, subjects’ data are excluded only after treatment discontinuation based on the prescribed cut off days (see Section 0).

Efficacy tables are summarized for subjects “prior to rescue and treatment discontinuation” and “regardless of rescue and treatment discontinuation”. For analyses based on “prior to rescue and treatment discontinuation” subjects’ data will be included up to the earliest of the start of rescue medication, or last dose of study medication including the cuts off allowances described in Section 0. For analyses “regardless of rescue and treatment discontinuation” all subjects’ data will eligible for inclusion in the analyses.

This model assumes that the time course of the endpoint values for subjects who discontinue treatment or are rescued at a specified time point is consistent with the time course for subjects who are ongoing at that time point.

While utilizing models such as ANCOVA, for Hb1Ac analysis of change from baseline, the measurement closest to the target date is assigned as the Week 52 measurement and will be used. If no Week 52 measurement is available (subject has discontinued before Week 52, or measurement not taken at Week 52, though subject was not discontinued), then the last available earlier post-baseline measurement will be used (LOCF). For subjects who started rescue medication prior to Week 52, their last post-baseline measurement taken prior to or on the date of the first dose of rescue medication will be used in the “prior to rescue medication” analyses.

For safety analyses based on “regardless of rescue medication”, which exclude data after treatment discontinuation, all data will be eligible to be used until the prescribed cut off (see Section 0).

For urinary albumin to creatinine ratio (uACR) shift tables, if no week 52 data are available for a subject, then last available observation prior to week 52 is used.

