7.5 Efficacy

7.5.1 Overall Efficacy Summary

All efficacy analyses will be performed using the Randomized Subjects data set. In addition, at the ST analysis, the primary efficacy analysis will be performed using the Evaluable Subjects data set if > 10% of subjects in any treatment group have relevant protocol deviations.

Unless otherwise specified, all analyses will be done using values prior to rescue/intensification of treatment or treatment discontinuation (plus a tolerance window after last dose as detailed in Section 0). For the endpoint of the proportion of subjects achieving a therapeutic glycemic response at Week 52/Week 156, all available data will be used, but subjects rescued prior to Week 52/Week 156 will be treated as non-responders.

The comparator (glimepiride plus metformin) will be tested against saxagliptin, in co-administration with dapagliflozin plus metformin, for the primary efficacy endpoint at the alpha = 0.05 level (two-sided). The secondary efficacy endpoints will then be tested sequentially, each comparison tested at the alpha = 0.05 level (two-sided). The following testing hierarchy (shown in order of the step-wise testing sequence) for treatment comparisons will be used:

- Mean change from baseline in HbA1c at Week 52 (primary endpoint).
- Mean change from baseline in total body weight at Week 52.
- Percent of subjects achieving a therapeutic glycemic response, defined as HbA1c < 7.0%, at Week 52.
- Mean change from baseline in systolic blood pressure (SBP) at Week 52.
- Time to treatment intensification (addition of insulin or other glucose-lowering agent for rescue therapy or discontinuation for lack of glycemic control) during the 52-week double-blind treatment period.

If all the above five comparisons performed for the short-term analysis are statistically significant, the following two comparisons will be tested sequentially for the short-term plus long-term analysis:

- Time to treatment intensification (addition of insulin or other glucose-lowering agent for rescue therapy or discontinuation for lack of glycemic control) during the 156-week treatment period.
- Proportion of subjects achieving a therapeutic glycemic response, defined as HbA1c < 7.0%, at Week 156

Analyses of exploratory endpoints specifically designed for sub-studies (CGM and MRI-PDFF) will be performed using the subsets of the Randomized Subjects data set for the sub-studies.

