7.5.4 Secondary Efficacy Analyses

In order to protect the overall type I error rate, the interpretation of the statistical significance of treatment comparisons for each secondary efficacy endpoint will be done using a step-wise procedure as outlined in Section 7.5.1

The ordered list of secondary endpoints for the sequential testing procedure is:

- Mean change from baseline in total body weight at Week 52.
- Percent of subjects achieving a therapeutic glycemic response, defined as HbA1c < 7.0%, at Week 52.
- Mean change from baseline in SBP at Week 52.

- Time to treatment intensification (addition of insulin or other glucose-lowering agent for rescue therapy or discontinuation for lack of glycemic control) during the 52-week double-blind treatment period.
- Time to treatment intensification (addition of insulin or other glucose-lowering agent for rescue therapy or discontinuation for lack of glycemic control) during the 156-week treatment period.
- Proportion of subjects achieving a therapeutic glycemic response, defined as HbA1c < 7.0%, at Week 156

The analysis of change from baseline for total body weight and SBP will be performed using the same longitudinal repeated measures model as for the primary efficacy endpoint.

The proportion of subjects achieving a therapeutic glycemic response (defined as HbA1c < 7.0%) at Week 52 and Week 156 will be summarized by treatment group and compared between treatment groups using logistic regression, adjusting for baseline Hb1Ac. The 95% confidence intervals for the response rate within each treatment group, as well as for the difference in response rates between treatment groups, will be calculated with adjustment for baseline HbA1c. Subjects who are rescued, discontinued or have missed measurements at Week t (t = 52 and 156, respectively) will be considered as not achieving glycemic response.

Time to treatment intensification will be analyzed using a Cox proportional hazards model. Estimates of the hazard ratio and 95% confidence intervals will be provided. This analysis will be performed only when there are at least 10 events in each treatment group. Kaplan-Meier estimates will be calculated and plotted by treatment group. For the analysis during 52 / 156 weeks, all subjects will be censored at 52 / 156 week short-term / long-term treatment period if treatment intensification has not occurred by then. Subjects rescued at Week 52 / 156 visit will be counted as having an event for the analysis.

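### The time-to-intensification analyses give no censoring date before Week 52/156 for subjects who withdraw consent or are lost, so as written they count as event-free to the end

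*Protocol*

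**What the plan says.** Protocol 8.3.2 and SAP 4.2 define the event as a glucose-lowering agent added as rescue, or stopping for lack of glycemic control. It is analyzed over 52 and over 156 weeks with a Cox model and Kaplan-Meier curves.

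On censoring, Protocol 8.4.2.2 states that "all subjects will be censored at 52 / 156 weeks if treatment intensification has not occurred by then". SAP 7.5.4 states that "all subjects will be censored at 52 / 156 week short-term / long-term treatment period if treatment intensification has not occurred by then". Both then count subjects rescued at the Week 52 or Week 156 visit as events. SAP 7.1.7, on Kaplan-Meier estimation, has no censoring rule, and the cut-off table in SAP Section 12 has no row for this endpoint.

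Follow-up is meant to continue after study drug stops: "All subjects who discontinue from treatment should remain in the study and comply with protocol-specified follow-up procedures" (Protocol 3.1). The protocol also foresees that it may not:
- Protocol 3.6.1, on withdrawal of consent: "The only exception to this is when a subject specifically withdraws consent for any further contact with him/her".
- Protocol 3.6.2 covers loss to follow-up and asks for a last known alive date, which is not linked to any analysis.
- Protocol 3.6 allows, where scheduled participation is impossible, that the subject may "be contacted by telephone 4 weeks after discontinuation of study drug to evaluate the following safety assessments: AEs and hypoglycemia events".

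The SAP's general data rule is: "Unless otherwise specified, all analyses will be done using values prior to rescue/intensification of treatment or treatment discontinuation" (7.5.1). SAP 7.1.1.3 says that "data will be included up to the earliest of the start of rescue medication, or last dose of study medication". Neither names this endpoint.

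**The concern.** A subject who withdraws consent at Week 30 has unknown intensification status from then on. The rule as written treats that subject as known to be event-free to Week 52 or Week 156. Observed events are then divided by risk sets that contain people who can no longer have an observed event. Incidence is understated in each arm in proportion to its loss, and the hazard ratio is distorted if the arms lose subjects at different rates.

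The contrast within Protocol 8.4.2.2 is telling. For the responder endpoint, the same section says how rescued, discontinued and missing subjects are handled. For time to intensification, no such rule is given.

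A related detail is the treatment of agents started after study drug is stopped for another reason. If the general rule in SAP 7.5.1 governs, such subjects have no usable status after stopping, yet the censoring sentence still carries them to Week 52/156. The two passages need to agree.

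**Working it through.** **The plan's own figures.** The documents give no event rate, event count or power for this endpoint. The sample size for the primary endpoint reproduces: 2 × (1.960 + 1.282)² × 1.1² / 0.35² = 207.6, so 208 evaluable per arm, and 208 / 0.95 = 219 against the stated 220 (Protocol 8.1). It supplies two inputs here: 220 per arm, and 5% as the only post-randomization attrition figure.

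**Assumptions.** Intensification by Week 156 is 50%, and loss over 156 weeks is varied. Both times are exponential and independent of each other. With Week 156 as the time unit, λ = −ln(1 − 0.50) = 0.6931 and μ = −ln(1 − loss).

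**Incidence under the rule as written.** If nobody is censored before Week 156, Kaplan-Meier reduces to the proportion with an observed event, F = λ/(λ+μ) × (1 − e^−(λ+μ)).
- 5% loss: μ = 0.0513; 0.6931/0.7444 × (1 − 0.50 × 0.95) = 0.931 × 0.525 = 48.9%.
- 20% loss: μ = 0.2231; 0.6931/0.9163 × (1 − 0.50 × 0.80) = 0.756 × 0.60 = 45.4%.

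**Hazard ratio, hand check (true value 1).** Use ln(1 − F₁)/ln(1 − F₀), experimental arm first.
- 10% v 5% loss: F = 47.74% and 48.88%; 0.649/0.671 = 0.97.
- 30% v 15% loss: F = 42.92% and 46.58%; 0.561/0.627 = 0.89.

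**Hazard ratio, Cox model.** The large-sample value solves ∫[f₁ − (f₁+f₀) e^β S₁/(e^β S₁ + S₀)] dt = 0, with f = λe^−(λ+μ)t and S = 1 − λ/(λ+μ) × (1 − e^−(λ+μ)t).

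| Loss, experimental v glimepiride | True 1.00, Week 156 | True 1.00, Week 52 | True 0.70, Week 156 |
|---|---|---|---|
| 5% v 5% | 1.000 | 1.000 | 0.701 |
| 10% v 5% | 0.971 | 0.991 | 0.682 |
| 20% v 20% | 1.000 | 1.000 | 0.705 |
| 30% v 15% | 0.905 | 0.968 | 0.640 |
| 15% v 30% | 1.104 | 1.034 | 0.779 |

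With S replaced by e^−(λ+μ)t, which is censoring at last follow-up, every row returns the true value.

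**Testing.** In 10,000 simulated trials per scenario (220 per arm, no effect at either time, earlier steps assumed passed), the Week 156 test taken alone rejects in about 5% with equal or 10% v 5% loss, and in about 10 to 11% with 30% v 15% loss in either direction. Step 6 is reached only "If all the above five comparisons performed for the short-term analysis are statistically significant". Steps 5 and 6 both reject in 1.4% to 2.5% of these trials, and in 1.1% to 2.8% when incidence ranges from 30% to 70%.

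**Baseline HbA1c in the Cox model (separate check).** Assumptions: 2,500 trials, conditional hazard ratio 0.70, 15% loss per arm, baseline SD 0.8%. Week 156 power without v with the covariate is 66% v 66% if it is not prognostic, 65% v 67% at a hazard ratio of 1.5 per 1%, and 62% v 68% at 2.0 per 1%.

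**The case against.** The strongest reply is that the sentence only fixes the administrative end of two nested analyses. Kaplan-Meier with Greenwood intervals (SAP 7.1.7) would be needless if nobody could leave early, and programmers commonly censor at last contact. That reading is plausible, and it is why the point is minor. It is still not what the text says: both documents write of all subjects, and the SAP's mention of the treatment period could equally mean each subject's own period.

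Other parts of the reply stand:
- The larger shifts need 30% v 15% loss, which has no source in the documents. At equal 5% loss the hazard ratio does not move.
- Subjects who stop drug are asked to stay in follow-up, and Table 5.1-4 includes review of concomitant medication, so only true loss of contact counts.
- Death without intensification is not unknown status. Keeping that subject event-free gives the right cumulative incidence, whereas censoring at death in Kaplan-Meier overstates it.
- Censoring at last follow-up is exact above only because simulated loss was independent of event risk. When a shared frailty linked loss and events in the experimental arm only (30% v 15% loss, true value 1, log-normal SD 0.7 or 1.0), it gave about 0.95 and 0.88. The rule as written was worse, at 0.85 and 0.79.
- Whether agents started off drug count is largely answered. Rescue is defined as an addition to blinded treatment (Protocol 3.5.2), the endpoint requires an agent given as rescue, and SAP 6.1 places early discontinuers in a non-treatment phase. What is missing is a sentence that ties this to the censoring date.

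**Conclusion.** Minor, but real. As written, the rule understates intensification incidence whenever contact is lost, by about 1 point at 5% loss and 5 points at 20% for an assumed 50% incidence. It biases the hazard ratio in favour of the arm with more loss: 3% at 10% v 5%, about 10% at 30% v 15%, and less at Week 52. All event and loss rates are assumptions.

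Two stronger inferences are not supported. A reader might conclude that the result is tilted toward saxagliptin plus dapagliflozin; the documents give no loss rates by arm, so the direction is unknown. A reader might also take the 10 to 11% stand-alone rejection as an inflated confirmatory error. Step 6 is gated by step 5, and with no effect at either time both reject in under 3% of the trials modelled. A real Week 52 effect that has gone by Week 156 was not modelled, so that case is open. The primary endpoint and steps 2 to 4 are untouched.

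**What to change.** In SAP 7.5.4, state: *Subjects without treatment intensification are censored at the earlier of Week 52/156 and the last date on which intensification status was assessed.* Then:
- Report completeness of follow-up by arm, and say that this censoring removes the bias only if loss is unrelated to the risk of intensification given treatment.
- Treat death without intensification as a competing event, for example with cumulative incidence curves, and not as loss.
- Reconcile the handling of agents started after stopping study drug with the censoring date, consistent with Protocol 3.5.2 and 8.3.2 and SAP 6.1 and 7.5.1. If they do not count, the censoring date cannot fall after treatment discontinuation, and that censoring may itself be informative.
- Include baseline HbA1c as a continuous covariate in the Cox model, as the responder analysis already does. The gain is modest: 0 to 6 points of power at Week 156 under the assumptions above.

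The cost is a few lines in the SAP, an entry in SAP Section 10 and one follow-up table; visit, contact and medication dates are already collected. Changing the protocol text as well would need ethics review (Protocol 9.1.1). SAP Version 3 was written while the short-term report was being prepared, so any change to an already reported Week 52 analysis should be labelled post hoc. The Week 156 change should be dated before the final database lock.

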8.4.2.3 Other Efficacy Analyses

Analyses for other efficacy objectives will use the same methodology for continuous endpoints as described above. For composite response endpoints (glycemic control without hypoglycemia or weight gain), the proportion of subjects achieving targets will be summarized by treatment group without adjustment for baseline. All exploratory endpoints will not be statistically tested.

8.4.3 Safety Analyses

The number and percent of subjects with at least one adverse event will be summarized for each treatment group, including summaries of AEs, SAEs, AEs leading to discontinuation of study medication, and AEs of special interest. Summaries will include the number of subjects with events by specified System Organ Class (SOC) and Preferred Terms (PTs).

Additionally, the incidence of AEs and frequency of recurring AEs will be summarized for each treatment group for both frequent events (occurring in at least 5% of subjects) and for selected AEs of special interest.

Values and changes from baseline at each scheduled time point for clinical laboratory parameters, body weight, and vital signs, including seated BP and HR, will be summarized by treatment group using descriptive statistics. The normality/abnormality of ECG tracings, as determined by the investigator, will be summarized by shift tables overall and by ECG tracing at baseline. The number and percent of subjects with laboratory values meeting marked abnormality criteria will be summarized for each treatment group. Other safety assessments including serum creatinine and CrCl by the Cockcroft-Gault equation and eGFR by the Modification of Diet in Renal Disease (MDRD) equation will be summarized by treatment group using descriptive statistics of values and changes from baseline at each scheduled time point.

Safety analyses for the 52-week double-blind treatment period and combined short-term and long-term treatment periods will be performed using the Treated Subjects data set, including data after rescue. Additional analyses for adverse events and laboratory marked abnormalities will be performed excluding data after rescue. The primary analyses of events of hypoglycemia will be performed excluding data after rescue.

